## 2.2.6 Instrument Separation

After decades of research and development, intracanal breakage of root canal instruments continually causes endodontists and patients considerable anxiety. Removal of separated instruments requires additional dentin removal and irrigation which generally results in perforated or severely weakened roots. An 18-month study involving 7,159 discarded rotary NiTi instruments from 14 endodontists worldwide reported a frequency of 5% instrument separation. A review of the literature reveals that the mean prevalence of retained fractured endodontic hand instruments (mostly stainless steel files) is approximately 1.6%, with a range of 0.7% to 7.4%. However, it bears mentioning that much of the published literature is comprised of outcome studies that do not specifically evaluate prevalence of instrument fracture. The mean clinical fracture frequency of rotary NiTi instruments is approximately 1.0% with a range of 0.4 to 3.7%. Suter et al. analyzed the probability of removing fractured instruments from root canals. During an 18-month study, they found that a fractured instrument was left inside 1% of all the root canals treated.

## 2.2.7 Extrusion of Debris into the Periapical Tissue

During preparation, irrigant (i.e. sodium hypochlorite) and debris (e.g. bacteria, dentin debris, and necrotic tissue) are often extruded into the periradicular region, leading to periapical inflammation and postoperative flare-ups. It is known that inflammatory reactions can cause

bone resorption, edema, and pain. All preparation techniques and instruments have been reported to be associated with extrusion of infected debris, even when preparation is maintained short of the apical terminus. There are several studies analyzing the apical debris extrusion resulting from different instrument types and instrumentation techniques. Various conclusions have been drawn, but all studies agree that, regardless of the instrument type or the technique, currently practiced RCT is associated with some level of apical debris extrusion, which affects the healing process significantly.

## 2.2.8 Extrusion of Sodium Hypochlorite into the Periodontal Tissues

Root canal irrigation with sodium hypochlorite (NaOCI) plays an important role in the debridement and disinfection of the root canal system and is an integral part of traditional root canal procedures. However, sodium hypochlorite has a pH of approximately 11 to 12, causing injury upon entering the body. If the irrigating solution permeates the periodontal tissues, it can result in inflammation, postoperative pain, and extended healing. Other commonly reported responses include severe pain, a rapidly developing edema, hematomas, necrosis, and abscesses. Several reports of the effects of sodium hypochlorite accidentally spreading beyond the interior regions of the tooth can be found in the literature. Additionally, instrumentation and the enlargement of canals have a significant effect on the penetration of sodium hypochlorite through the apical foramen. Salzgeber and Brilliant showed that instrumentation beyond a size 35 may allow penetration of irrigant beyond the apex and into periapical tissue.

## 2.3 Healing Rates for Traditional Root Canal Therapy

While the literature presents many different definitions of healing, any future endodontic clinical studies should utilize a healing endpoint based upon both clinical and radiographic findings. The radiographic finding should be based upon the periapical index score, with PAI 1 or 2 indicating success. Additionally, no clinical signs or symptoms should be present. Separating complete healing and incomplete healing will also more clearly present study results.

Success rates over time varied widely across the literature. Generally, most healing had occurred 1 year following root canal treatment, though healing was shown to take up to 4 years or more. Thus, success rates should also be presented at each time-point studied and not just a cumulative number over a range of follow-up periods. An approximate success rate for 1 year follow-up would be 68-70% while that success rate would increase to 80-85% after four years.

While effective chemomechanical canal preparation is extremely important, the literature indicated other factors significantly affected long-term prognosis for the patient. If a patient presented with apical periodontitis and had a periapical lesion, the long-term success was significantly lower. Thus, including a large number of patients with a pre-operative periapical radiolucency could result in lower long-term success rates. Effective obturation to within 2 mm within the radiographic apex and effective coronal restorations also improved long-term success. The number of roots treated and mid-treatment complications could also impact success rates. These facts highlight the importance of choosing the appropriate patient

population and standardizing the treatment regimen in clinical studies so that the variable being studied can be reliably assessed.

While a number of studies have been published regarding the healing and success rates following root canal treatment, the quality of this literature is generally less than other medical disciplines. A dearth of randomized, controlled trials exists in endodontic research, and a large number of retrospective studies are published. Finally, the lack of standardization of study design and clinical endpoints across studies makes the comparison of results between studies difficult at best. *(See Appendix I. Healing Literature Report)* 

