## 13.1 Sample Size

All patients will receive root canal therapy with the Sonendo GentleWave System and will be subsequently followed for 24 months post procedure. A sample size of 108 subjects, assuming a 20% lost to follow-up or Treatment Incomplete Cohort rate, will result in approximately 86 subjects who would be evaluable for the primary efficacy endpoint. A sample size of 86 evauable subjects provides approximately 90% power to detect a difference between a 85% response rate for subjects using the Sonendo GentleWave System against a null hypothesis of a 70% response rate based on data presented in literature for traditional root canal therapy, using a two-sided binomial test at the 5% level of significance.

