## 13.4 Method for the Analysis of Primary Effectiveness Parameter

The primary effectiveness analysis will be based on Healing at twenty-four (24) months for Treatment Complete Cohort.

The proportion of subjects with healing, along with the exact 95% confidence interval, will be provided for healing at 24 months.

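### The plan does not separate or standardise the 24-month result by baseline periapical lesion, so a lesion mix unlike the literature's could move the comparison with 70% in either direction.

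*Combined protocol and SAP*

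**What the plan says.** Section 2.3 (healing rates for traditional therapy) identifies baseline lesion status as prognostic: "If a patient presented with apical periodontitis and had a periapical lesion, the long-term success was significantly lower". It draws the consequence for case mix too: "including a large number of patients with a pre-operative periapical radiolucency could result in lower long-term success rates". It ends by stressing the choice of patient population.

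Section 13.1 (sample size) rests the trial on one undivided figure, a "null hypothesis of a 70% response rate based on data presented in literature for traditional root canal therapy". The alternative is an "85% response rate for subjects using the Sonendo GentleWave System".

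Section 13.4 (primary effectiveness) plans one overall estimate: "The proportion of subjects with healing, along with the exact 95% confidence interval, will be provided for healing at 24 months". It contains no comparison with 70%; that appears only in 13.1.

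Elsewhere in the protocol:
- Sections 5.1 to 5.4 admit any first or second molar indicated for root canal therapy. No criterion, cap or quota refers to PAI or a periapical lesion.
- Section 4.0 describes a literature-controlled study in which every patient receives the device.
- Section 7.4.4 collects PAI at Baseline, scored by independent reviewers blinded to site, subject and visit.
- Section 13.8 names the only subset analysis, an optional one by pre- and post-market enrollment.
- Section 13.0 defers analysis details to a statistical analysis plan. No separate text of that plan is in the documents reviewed.

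**The concern.** With no concurrent arm, the 70% is a fair reference only if the enrolled teeth resemble those behind it on the factors that drive success. The protocol names baseline lesion as such a factor, but neither eligibility nor the analysis controls for it.

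The endpoint also asks different things of the two kinds of tooth. A tooth that starts at PAI 1 or 2 meets the radiographic part of the healed definition by not getting worse. A tooth that starts at PAI 3 to 5 must improve.

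If fewer lesion teeth enrol than in the literature, the overall rate can exceed 70% with no device effect. If more enrol, a real benefit can be hidden. One overall proportion cannot distinguish these cases from a true device effect.

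**Working it through.** **1. The plan's own figure.** Inputs from section 13.1: n = 86, null 70%, alternative 85%, "using a two-sided binomial test at the 5% level of significance".

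- Upper rejection limit: the smallest r with P(X >= r | 86, 0.70) <= 0.025 is r = 69, with tail probability 0.0223. The matching lower limit is 51, and the actual two-sided level is 0.0447.
- 69/86 = 80.2%, exact 95% CI 70.2% to 88.0%, just above 70%. For 68/86 the lower limit is 69.0%.
- Power: P(X >= 69 | 86, 0.85) = 91.4%. The protocol says "A sample size of 86 evauable subjects provides approximately 90% power", so its figure reproduces.
- Enrollment: 86/(1 - 0.20) = 107.5, rounded up to 108, as stated.

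The sample-size arithmetic is not at fault.

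**2. Effect of lesion mix with no device effect.** Let d be the success rate in no-lesion teeth minus that in lesion teeth, L the lesion share behind the 70%, and T the lesion share in the trial. Then

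expected trial rate = 0.70 + d × (L - T).

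The documents give none of d, L or T, so the values below are assumptions chosen to show the range and both directions.

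| d | L | T | Expected rate | P(X >= 69 of 86) |
|---|---|---|---|---|
| any | equal to T | equal to L | 70% | 2.2% |
| 5 points | 50% | 0% | 72.5% | 6.5% |
| 10 points | 50% | 20% | 73% | 7.9% |
| 20 points | 50% | 20% | 76% | 21.6% |
| 20 points | 50% | 0% | 80% | 54.3% |
| 20 points | 50% | 60% | 68% | 0.8% |

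Worked example, fourth row: 0.70 + 0.20 × (0.50 - 0.20) = 0.76.

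**3. Precision of a split.** If about 30% of the 86 teeth have a lesion (an assumption), the lesion stratum has 0.30 × 86 = 25.8, about 26 teeth. A result of 18/26 (69%) has an exact 95% CI of 48% to 86%. At a 20% share, 0.20 × 86 = 17.2, about 17 teeth, and 12/17 (71%) gives 44% to 90%.

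**The case against.** The strongest objection is that the lesion mix behind the 70% cannot be seen. Section 2.3 refers to the Appendix I literature report, whose text is not among the documents reviewed. The benchmark may come from a mix like the trial's, in which case there is no shift. This stands, and it is why no single size can be given.

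The gap may also be smaller on this endpoint than on the long-term success that section 2.3 describes. Section 3.1 counts healed or healing, and healing includes a reduced radiolucency, so a lesion tooth can succeed by shrinkage alone. This stands too: with a 5-point gap and a 50% benchmark share, the chance of reaching 69 never exceeds 6.5%.

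Section 13.3 summarises baseline characteristics and PAI is a secondary endpoint, so the lesion share may be reported anyway. That would describe the mix without linking it to outcome. A split could also sit in the separate analysis plan; in that case a cross-reference in 13.4 settles the point.

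A lesion split would not isolate the device effect by itself. Section 2.3 also names obturation level, coronal restoration, number of roots and mid-treatment complications.

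A reader might infer that a favourable case mix will by itself carry the trial past 70%. The documents do not support that. It needs a large gap together with a trial lesion share far below the literature's; neither is stated, and the shift could run the other way.

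**Conclusion.** The point holds as a gap in interpretation. As written, the plan leaves the comparison with 70% open to confounding by a factor the protocol itself calls prognostic, and the direction is not known in advance. In the illustrations, the chance of reaching 69/86 with no device effect runs from 0.8% at a true rate of 68% to 54.3% at 80%, against 2.2% when the mix matches. These figures rest on assumed gaps and lesion shares; they are not estimates of what will happen in this trial. The primary proportion can still be calculated, but a rate above or below 70% cannot be attributed to the device without knowing the lesion mix on both sides. The omission is certain only for the text reviewed.

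**What to change.** In section 13.4, pre-specify:

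- the 24-month rate with exact 95% CI separately for Baseline PAI >=3 and PAI <3;
- the lesion share and the number of subjects with no baseline PAI score (section 7.4.4 does not treat a missing score as a deviation and sets no window for scoring);
- a comparison of each stratum with a lesion-specific literature rate, or of the overall rate with a benchmark standardised to the enrolled lesion mix, where the Appendix I report allows;
- if it does not allow this, a plain statement that the comparison with 70% is not adjusted for case mix.

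Setting both strata beside the same 70% would not be enough, because each comparison would still be mismatched.

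The overall analysis can stay primary, and sample size and study conduct do not change. The cost is one table from assessments already scheduled, plus a return to the literature report. Stratum intervals will be wide, so the split is for interpretation and is not a new test. Fixing the PAI cut-point now avoids choosing it after the results are known.

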## 2.4 Sonendo GentleWave Technology Overview

The Sonendo GentleWave System (System) introduces a novel method of cleaning root canals that may be safer, less invasive, and more efficient. It has been designed to conserve more of the natural structure of the tooth and to minimize procedural and safety issues. The System, when used in combination with the Molar Handpiece (Figure 2), has been designed to clean root canals of molar teeth without requiring excessive enlargement of root canals. Traditional root canal therapy devices enter into the root canal of the tooth, whereas the System's treatment tube (guide tube) is designed to enter only to the pulpal chamber. It has been designed to clean the root canals remotely and simultaneously in a matter of minutes.

Figure 2: Illustrations of the Molar Handpiece applied to a molar tooth. The Handpiece delivers a stream of treatment fluid in such a way as to generate a set of physicochemical phenomena that effectively, yet safely, clean the pulpal space of the tooth.

The Sonendo GentleWave treatment is designed for use with minimal instrumentation of the root canals in order to facilitate obturation of the root canal system. It is also thought that by minimizing the shaping process, a large amount of tooth structure may be saved, as opposed to traditional practice, which typically removes this structure. In addition, the System may reduce the risks associated with instrumentation, i.e. ledge formation, instrument separation, and perforation. Unlike conventional root canal treatment, irrigation solutions are delivered into the root canal system without requiring the irrigation component (i.e. the needle) to be inserted inside each individual canal. With the System, the solution enters the tooth at about 1 mm above

the pulpal chamber floor. This alteration from traditional root canal therapy may minimize the risk of irrigant extrusion into the periapical tissues.

## 2.5 Device Description

The Sonendo GentleWave System (System) is comprised of two units: the Sonendo GentleWave™ Console (Console) and the Molar Handpiece (Handpiece). The Console prepares and delivers treatment fluid to the Handpiece. The Handpiece comes with additional accessories needed to interface the Handpiece to the Console and tooth.

The System delivers treatment fluid into the axis cavity of the tooth in such a way that it creates hydroacoustic waves within the treatment fluid accumulated inside the tooth. The treatment fluid delivered into the tooth removes organic tissues and smear layer from the root canal system. The Console aspirates the treatment fluid and organic/inorganic matter from the tooth into the Console waste canister. The Console is designed for use with a treatment fluid of 8-10% sodium hypochlorite (NaOCI) without surfactants, 17% neutral pH buffered ethylenediaminetetraacetic acid (EDTA), and distilled water.

All of the materials coming into contact with the patient and/or the treatment fluid have known biocompatibility and a history of acceptable use in medical device applications.

## 2.5.1 Console

The Console (Figure 3) is a semi-stationary unit designed to prepare and deliver treatment fluid to the Handpiece. It is comprised of a treatment fluid Delivery Hose, a Suction Hose, a Purge Port, Evacuation Tubing, a User Interface Screen, a distilled water Reservoir, an NaOCI Reservoir, an EDTA Reservoir, a Waste Canister, and a Foot Pedal. Similar to the dental handpieces currently used in dentistry, the System is activated by a foot pedal, which must remain depressed in order to operate the System.

The Console is made up of five functional subgroups of components:

1. Delivery System

The Delivery System is composed primarily of a pump. This pump operates in two cycles: a delivery cycle and a retraction cycle. During the delivery cycle, the piston moves forward in order to pump the treatment fluid through the outlet. The pump operates with two cylinders/pistons (continuous flow). During the retraction cycle, more water is drawn into the cylinder, readying the System for the upcoming cycle.

2. Mixing System

The Mixing System is designed to mix and prepare the treatment fluids NaOCl, water and EDTA at the prescribed concentrations.

3. Degassing System

The Degassing System is configured to reduce dissolved gasses from treatment fluids as they are passed through the degassing cartridge.

4. User Interface

A touch-panel screen is mounted on the outside of the Console and provides the operator with real-time feedback relating to the treatment progress.

5. Evacuation System

The Evacuation System is designed to prevent waste and treatment fluid from spraying or spilling from the Handpiece or tooth during normal operation. In addition, the fluid that passes through the System and into the Handpiece is then returned to the Console through the Evacuation System.

Figure 3. Example image of the Sonendo GentleWave System

The treatment fluid containers are connected to the System using standard quick-connects that are included in Food and Drug Administration's (FDA) U.S. Pharmacopeia (USP) Class VI list of established materials. The System is designed to comply with applicable electrical safety standards for medical electrical equipment. The user will activate and maintain operation of the System by depressing the foot pedal.

## 2.5.2 Molar Handpiece

The Molar Handpiece comes with the following accessory items which are needed, in addition to items commonly used in standard dental practice, in order to successfully carry out the Sonendo GentleWave treatment:

1. Molar Handpiece

The Handpiece consists of a quick-connect fitting to the delivery hose, fluid conduit, distal fluid chamber, nozzle, delivery tube, and clamshell plastic grip.

The Handpiece is designed to be a single use, disposable component. The Handpiece may be sterilized by a steam autoclave or gamma irradiation.

The Handpiece, containing proprietary features such as a nozzle and a treatment tube (also called a guide tube), delivers a stream of treatment fluid into the pulp chamber of the tooth. This is completed in such a way that it creates hydroacoustic waves within the treatment fluid accumulated inside the tooth. The treatment fluid is a low concentration sodium hypochlorite (NaOCI) solution, which is the most commonly used irrigant in traditional endodontic procedures for dissolution of organic matter and for added sterility. The stream of solution delivered into the tooth is designed to be dispersed and deflected by proprietary features at the distal end of the treatment tube. This is designed to create a safe yet effective circulation (irrigation) of the solution within the tooth. These physicochemical phenomena occurring inside the pulpal space may be powerful enough to remove all of the organic tissues and microorganisms from the root canals in just a few minutes, yet gentle enough not to affect the hard structure of the tooth or the periodontal tissues enclosing the roots. The used treatment fluid flows from the tooth into a Waste Canister rendering the procedure dry and contained.

The Handpieces are produced by approved suppliers based on Sonendo drawings and are inspected upon receipt. They are checked for dimensional accuracy, performance, production, and inclusion of appropriate material certifications in the shipment documentation.

2. Single Use Suction Hose

The single use Suction Hose is designed to suction air and fluids during the procedure. The Suction Hose is made from Tigon tubing and Policarbonate fittings.

3. Occlusal Plate

The Occlusal Plate features a handle, a circular area, and a pin protruding from the middle of the circular area. This pin helps locate the center of the tooth surface in order to facilitate locating the pulp chamber. The Occlusal Plate is used to form a flat surface, called an Occlusal Platform, so that the Handpiece can create a seal against it. The Occlusal Plate is made from polycarbonate.

4. Molar Tooth Caps

The Molar Tooth Caps are designed to provide the interface, the Occlusal Platform that is required for use with the Molar Handpiece when a substantial amount of the tooth's original structure is missing. In these situations, it is difficult to prepare the tooth for treatment with the Sonendo GentleWave System using the Occlusal Plate and impression material, so the Molar Tooth Caps may be used instead. The main components of the Molar Tooth Cap consist of polypropylene.

5. Set of Depth Gauges

The Depth Gauges are utilized to determine the depth of the pulp chamber. This is done to ensure the correct selection of the Sealing Cap size and correct positioning of the Treatment Tube (guide tube) within the pulp chamber. The Depth Gauges are made from polycarbonate.

6. Set of Sealing Caps

The Sealing Caps are designed to adapt the Molar Handpiece to different sized teeth. Each Sealing Cap is designed to properly position the Handpiece with respect to the floor of the pulp chamber. The Sealing Caps are made from polycarbonate, medical grade adhesives, silicone and/or polycarbonate.

## 2.5.3 Treatment Fluids

The three treatment fluids utilized during the System operation are sodium hypochlorite (NaOCI), ethylenediaminetetraacetic acid (EDTA) and distilled water. All fluids are introduced for treatment through the Console and Handpieces.

The first treatment fluid is a NaOCI solution. NaOCI is the most commonly utilized irrigation fluid during traditional root canal therapy, which is typically introduced via a dental syringe. This solution is prepared by the Console, which mixes distilled water and regular 8-10% NaOCI.

In addition, the root canals will be irrigated with EDTA solution. This solution is prepared by the Console, which mixes distilled water and 17% EDTA. The System automatically introduces EDTA into the tooth, while standard dental practice uses a dental syringe to release EDTA.

